4. INVESTIGATIONAL PLAN/STUDY DESIGN

4.1 Study Design Overview

This study will be carried out as a single institution, single arm phase I/II unblinded trial. A maximum of 20 patients will be enrolled. Each patient will be treated with nivolumab, ipilimumab and stereotactic body radiation therapy. Nivolumab will be continued for a total of 12 cycles, unless evidence of unacceptable toxicity, disease progression or withdrawal of patient consent were to occur.

4.2 Study Schema

Note: refer to Dosing and Administration (Section 5.1.1) for further details on treatment scenarios.

Clinical Study Protocol RG1718030
Drug Substance: Nivolumab and Ipilimumab
IND Number:140818
Protocol version 3.0 April 17, 2019

Both ipilimumab and nivolumab are FDA approved, and the safety profile of both agents have been extensively studied. However, because the combination with radiation has not been previously studied, the first 6 patients of this study will represent the initial run-in phase of the triplet combination of nivolumab, ipilimumab and palliative radiation. The initial doses of ipilimumab and nivolumab will be administered on day 1 of therapy.

Stereotactic radiation will be initiated on Week 3 of treatment. SBRT will be delivered to a total dose of 24 Gy, given in 3 fractions of 8Gy every other day. Treatment will be continued according to the study schema unless patient withdraws consent, has confirmed disease progression, and/or develops toxicity that results in treatment discontinuation.

Enrollment will be halted until these first 6 patients complete the first 12 weeks of treatment and acute toxicities will be reviewed. If more than 2 DLTs (to be defined in Section 5.1.2) are noted in this six patient cohort, a dose modification will be implemented (Section 5.1.1) for the remaining 14 patients who will be enrolled in the expansion cohort.

Serum correlative studies will be collected at the following timepoints: at baseline, prior to week 8, and prior to week 16 of treatment. Archived formalin fixed paraffin embedded tissue (obtained in the 12 months prior to trial enrollment) will be collected from patients enrolled. If the patient does not have archived tissue available, a fresh biopsy will be obtained. Tissue requirement will be waived if deemed contraindicated or not clinically available/accessible for resection per the treating physician (PI approval required).

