Study Design

This is a single arm, open label, prospective study evaluating the safety and clinical efficacy of the combination of nivolumab, ipilimumab and hypofractionated palliative radiation therapy (SBRT) in patients with advanced salivary gland cancer.

Patients enrolled will receive the following treatment (see Section 5.1.1):

1. Nivolumab 3mg/kg IV Q 2 weeks x 12 doses followed by Nivolumab 480 mg IV Q4 weeks x 8 doses
2. Ipilimumab 1 mg/kg IV Q6 weeks x 4 doses
3. Hypofractionated radiation therapy (SBRT) given to a total dose of 24Gy given in 3 fractions every other day over 1 week and initiated 2 weeks after the first dose of nivolumab and ipilimumab. The target lesion will be a local/regional or metastatic disease site that per the multidisciplinary head and neck team, requires local control for palliation and/or prevention of impending symptoms.

Both nivolumab and ipilimumab have well established toxicity profiles as a single agent and in combination. However, since the combination of nivolumab, ipilimumab and palliative radiation has not previously been described or studied, the first 6 patients who will be enrolled in this study will represent the initial safety run-in phase. Patients will receive full dose nivolumab and ipilimumab. Enrollment will be halted until these first 6 patients complete the first 12 weeks of treatment and acute toxicities will be reviewed. If more than 2 DLTs (to be defined in Section 5.1.2) are noted in this 6 patient cohort, a dose modification will be implemented (Section 5.1.1) for the remaining 14 patients who will be enrolled in the expansion cohort. Enrollment period is 24 months and duration of the trial 48 months.

Study Population

The study aims to enroll patients with salivary gland carcinomas (WHO, 2005), who are not candidates for curative intent therapy and who have a target lesion (either local/regional or distant metastatic site involving the lung and/or bone), that requires local control for palliation, as determined by a multidisciplinary team.

Inclusion Criteria:

1. Histologically proven salivary gland carcinoma (WHO, 2005) arising from a previous head and neck primary site, and located within the head and neck region, lung or bone, and who are not candidates for curative intent therapy.
2. ≥ 18 years old at the time of signing informed consent.

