5. TREATMENT

5.1 Systemic Therapy

5.1.1 Dosage and Administration

The treatment to be used in the run-in phase (initial 6 patients) of this trial is outlined in the table below. If ≤ 1 DLT is observed in the run-in phase, then the remaining 14 patients will be provided treatment per the following:

Drugs	Dose/Potency	Dose Frequency	Route of Administration	Regimen/Treatment Period
Weeks 1-24				
1. Nivolumab	3 mg/kg	Q2 weeks	IV infusion	Maximum of 12 doses
2. Ipilimumab	1mg/kg	Q6 weeks	IV infusion	Maximum of 4 doses
Weeks 25-52				
1. Nivolumab	480mg IV flat dose	Q4 weeks	IV infusion	Maximum of 8 doses

If 2 or more DLTs (defined in Section 5.1.2) are observed in the run-in phase, the following treatment will be used for the remaining 14 patients to be treated on the clinical trial protocol:

Drugs	Dose/Potency	Dose Frequency	Route of Administration	Regimen/Treatment Period
Weeks 1-24				
1. Nivolumab	3 mg/kg	Q4 weeks	IV infusion	Maximum of 6 doses
2. Ipilimumab	1mg/kg	Q8 weeks	IV infusion	Maximum of 3 doses
Weeks 25-52				
1. Nivolumab	480mg IV flat dose	Q6 weeks	IV infusion	Maximum of 4 doses

Patients who experience a DLT in the run-in phase, will have dose interruptions/reductions as outlined in Section 5.1.3.

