5.1.2 Definition of DLT

Dose-limiting toxicities (DLTs) will be evaluated during the run-in phase consisting of the first 6 patients enrolled in this trial. The period for evaluating DLTs will be from the time of first administration of nivolumab and ipilimumab until 12 weeks. Adverse event monitoring will continue for these subjects throughout the course of their treatment as outlined in the Schedule of Study Assessments, these adverse events will include potential XRT related toxicities. Subjects who do not remain on the study up to this time for reasons other than DLT will be replaced with another subject. Grading of DLTs will follow the guidelines provided in the Common Terminology Criteria for Adverse Events (CTCAE) version 5.0.

A DLT will be defined as any Grade 3 or higher toxicity that occurs during the DLT evaluation period. Toxicity that is clearly and directly related to the primary disease or to another etiology is excluded from this definition. The following will be DLTs:

- Any Grade 4 irAE
- Any \geq Grade 3 colitis
- Any Grade 3 or 4 noninfectious pneumonitis irrespective of duration

- Any Grade 2 pneumonitis that does not resolve to \leq Grade 1 within 3 days of the initiation of maximal supportive care
- Any Grade 3 irAE, excluding colitis or pneumonitis, that does not downgrade to Grade 2 within 3 days after onset of the event despite optimal medical management including systemic corticosteroids or does not downgrade to \leq Grade 1 or baseline within 14 days
- Liver transaminase elevation $> 8 \times$ ULN or total bilirubin $> 5 \times$ ULN
- Any \geq Grade 3 non-irAE, except for the exclusions listed below
 - Grade 3 fatigue lasting \leq 7 days
 - Grade 3 endocrine disorder (thyroid, pituitary, and/or adrenal insufficiency) that is managed with or without systemic corticosteroid therapy and/or hormone replacement therapy and the subject is asymptomatic
 - Grade 3 inflammatory reaction attributed to a local antitumor response (e.g., inflammatory reaction at sites of metastatic disease, lymph nodes, etc.)
 - Concurrent vitiligo or alopecia of any AE grade
 - Grade 3 infusion-related reaction (first occurrence and in the absence of steroid prophylaxis) that resolves within 6 hours with appropriate clinical management

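### Run-in entry does not pause when the DLT count reaches its trigger, so patients can still start the original schedule after the run-in decision is fixed

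*Combined protocol and SAP*

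**What the plan says.** The synopsis (Study Design) defines the cohort: "the first 6 patients who will be enrolled in this study will represent the initial safety run-in phase". Section 4.2 repeats this and sets the halt: "Enrollment will be halted until these first 6 patients complete the first 12 weeks of treatment and acute toxicities will be reviewed".

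Section 5.1.1 assigns one schedule to the whole cohort, with no condition on DLTs already seen: "The treatment to be used in the run-in phase (initial 6 patients) of this trial is outlined in the table below". The consequence of the count falls on later patients only. In Section 4.2 it reads "a dose modification will be implemented (Section 5.1.1) for the remaining 14 patients who will be enrolled in the expansion cohort".

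The trigger is given in two forms. Section 4.2, like the synopsis, has "If more than 2 DLTs (to be defined in Section 5.1.2) are noted in this six patient cohort". Section 5.1.1 has "If 2 or more DLTs (defined in Section 5.1.2) are observed in the run-in phase".

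Under Section 5.1.2 each patient is assessed "from the time of first administration of nivolumab and ipilimumab until 12 weeks". Patients who leave early for reasons other than a DLT, or who receive too little of the day 1 infusion and have no DLT, are replaced.

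**The concern.** The run-in exists because the three-part combination had not been studied before. Its decision depends on a count that can only rise: the replacement rules in Section 5.1.2 remove only patients without a DLT. If the trigger is met by the first few patients, later run-in entries cannot change what happens to the expansion cohort. As written, those patients may still be entered on the schedule that has already met the protocol's own criterion for modification. Replacements can add further run-in starts.

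No other rule closes the gap:

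- **Section 8.4** halts enrolment only when more than three patients have Grade 4 or higher drug-related toxicity. Many DLTs are Grade 3, and unresolved Grade 2 pneumonitis also counts, so the DLT trigger can be met without any Grade 4 event.
- **Section 3** provides a weekly team review but attaches no enrolment action to the DLT count.
- **Section 9** provides DSMC review as needed, again not tied to the DLT count.

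**Working it through.** The plan gives no operating characteristics for the run-in rule, so there is no figure of its own to reproduce.

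**Inputs from the documents.** Run-in of 6; maximum of 20 patients; enrolment period of 24 months; DLT window and enrolment halt of 12 weeks; trigger of at least 2 (Section 5.1.1) or at least 3 (synopsis, Section 4.2).

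**Assumptions.** At most one DLT per patient, onset uniform over the 12 weeks, evenly spaced entry, DLT recognised at onset. The DLT rate p is not stated, so 20% to 50% is shown. The 30% in the sample-size section is a planning rate for all Grade 3 or higher acute drug-related toxicity. It is only a guide, because the DLT definition excludes several Grade 3 events.

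**Step 1: spacing.** 24 months is about 104 weeks. (104 − 12)/20 = 4.6 weeks per patient. Entries fall at weeks 0, 4.6, 9.2, 13.8, 18.4 and 23.0. The first three windows close at weeks 12, 16.6 and 21.2, all before patient 6 starts.

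**Step 2: chance that the trigger is met in all six at p = 30%.**

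- At least 2: 1 − 0.7⁶ − 6(0.3)(0.7⁵) = 1 − 0.118 − 0.303 = 58%.
- At least 3: also subtract 15(0.3²)(0.7⁴) = 0.324, leaving 26%.

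**Step 3: upper bound on a late entry at p = 30%.** A late entry requires the trigger to be met among the first five.

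- At least 2 of 5: 1 − 0.7⁵ − 5(0.3)(0.7⁴) = 1 − 0.168 − 0.360 = 47%.
- At least 3 of 5: also subtract 10(0.3²)(0.7³) = 0.309, leaving 16%.

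**Step 4: simulation with timing.** For each run, take the time of the 2nd or 3rd DLT and count run-in entries after it. A re-run with 400,000 runs per setting agreed with the figures below to within a percentage point.

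| True DLT rate | At least one late entry, trigger 2 or more | Same, trigger more than 2 |
|---|---|---|
| 20% | 19% | 3% |
| 30% | 36% | 10% |
| 40% | 54% | 20% |
| 50% | 70% | 34% |

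Among runs in which the trigger is met, the mean number of late entries across these rates is about 1.1 to 1.8 (2 or more) and 0.5 to 0.8 (more than 2). The 30% row lies below the bounds in step 3, as it must.

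**Step 5: sensitivity.**

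- Random entry at the same mean spacing, at rates of 30% and 40%: 31% and 46% (2 or more); 8% and 16% (more than 2).
- A 2-week lag in recognising a DLT, same rates: 32% and 48%; about 8% and 16%.
- About 3 patients a month, rate 30%: 9% and 1%.
- If one patient can contribute more than one DLT, which the wording does not rule out, the trigger could be met sooner and the figures would rise.

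**Step 6: Section 8.4 as a backstop.** It needs at least four patients. Even if the Grade 4 or higher rate were 30%, the chance of 4 or more among the first five is 5(0.3⁴)(0.7) + 0.3⁵ = 0.028 + 0.002 = 3.1%.

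**The case against.** The strongest reply is that a fixed cohort of six, reviewed together and applied to the expansion, is a recognised design and is described consistently in the synopsis and Sections 4.2 and 5.1.1. Later run-in patients are not uninformative: acute toxicities in all six are reviewed, and every enrolled patient enters the primary safety analysis. This stands in part. Those patients add safety information, but they cannot alter the run-in decision once the trigger is met.

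A reader might infer that reaching the trigger declares the original schedule unacceptable. The documents do not say so. The alternative in Section 5.1.1 uses the same two drugs at longer intervals, and the trigger calls for a modification in later patients.

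A reader might also infer that the plan obliges the team to keep enrolling. It does not. This is a single-centre trial with weekly adverse-event review, DSMC oversight and individual dose holds under Section 5.1.3.1, and nothing prevents a voluntary pause. The point is that nothing requires one.

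The size is also open to challenge, and this objection stands. The larger figures belong to the two-or-more trigger, even entry and immediate recognition. Many DLTs take days to establish, because the definition turns on failure to improve within 3 or 14 days or on a delay of more than 2 weeks to the second dose.

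**Conclusion.** The gap is real on the text: entry of run-in patients on the original schedule can continue after the protocol's own trigger for modification has been met. It exists under either trigger but is much smaller under the higher one. At planned accrual the probability of a late entry is appreciable with two or more and modest with more than two. It becomes small if the six patients enter quickly.

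The structural finding is firm. The percentages are illustrations that rest on an unstated DLT rate and on the entry and onset assumptions above. They do not support saying that late exposure will happen, or that run-in patients not yet entered should receive one schedule or the other. The documents are silent on that, and the sponsor must settle it.

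This is a cheap improvement to a safety rule, not an error that undermines the trial.

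**What to change.** 1. Reconcile the two DLT triggers (synopsis and Section 4.2 against Section 5.1.1), and say whether the count is of DLTs or of patients with a DLT.
2. State in the synopsis, Section 4.2 and Section 5.1.1 that enrolment pauses for the toxicity review as soon as the count reaches the reconciled trigger, even if fewer than six patients have been entered. Keep the existing halt after six when the trigger has not been reached.
3. Reconcile the wording on six run-in and 14 remaining patients, including in Section 5.1.2 and the Statistical Considerations, so that it says how run-in patients not yet entered are handled after an early review, and when that review takes place if entered patients are still within their 12 weeks. No schedule is proposed here.

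The cost is a few sentences and matching edits, with no extra patients or data. The one downside is that fewer than six patients may be observed on the original schedule, but only when the run-in decision is already determined.

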 - Grade 3 or 4 neutropenia that is not associated with fever or systemic infection that improves by at least 1 grade within 3 days. Grade 3 or Grade 4 febrile neutropenia will be a DLT regardless of duration or reversibility
 - Grade 3 or 4 lymphopenia
 - Grade 3 thrombocytopenia that is not associated with clinically significant bleeding that requires medical intervention, and improves by at least 1 grade within 3 days
 - Isolated Grade 3 electrolyte abnormalities that are not associated with clinical signs or symptoms and are reversed with appropriate maximal medical intervention within 3 days
- Grade 4 hematologic toxicity, not described in exclusions above
- Prolonged delay (>2 weeks) in initiating second dose of nivolumab or ipilimumab due to treatment-related toxicity
- Grade 5 toxicity, i.e., death

Dose modification/delays according to Section 5.1.3 will apply to the patients who experience DLTs in the run-in phase.

Immune-related AEs are defined as AEs of an immune nature (i.e., inflammatory) in the absence of a clear alternative etiology. In the absence of a clinically significant abnormality, repeat laboratory testing will be conducted to confirm significant laboratory findings prior to designation as a DLT.

During this DLT period, patients who received <90% of the nivolumab OR ipilimumab infusion on day 1 (e.g., because the infusion of either drug had to be discontinued due to an infusion reaction) and did not experience a DLT will not be taken into account in the assessment of the overall DLT rate for the phase I run-in cohort and will be replaced.

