8.4 STUDY STOPPING RULE

In keeping with the study primary endpoint, a stopping rule will be implemented in the unlikely event that the combination under study is deemed to have unacceptably high toxicities. Enrollment will be halted if more than 3 patients experience a Grade 4 or higher drug related toxicity (CTCAE v. 5) during the trial treatment period or up to 30 days after the last investigational drug infusion. The likelihood of observing more than 3 Grade 4+ drug-related adverse events is 80% if the true

rate is 20% and the likelihood is 91% if the true rate is 25%. This rule has an 83% chance of prematurely discontinuing trial enrollment after the 1st 10 patients are enrolled if the true rate of Grade 4 drug related toxicity is 40%. The study will be reviewed by the University of Washington/Fred Hutch Cancer Consortium Data and Safety Monitoring Committee (DSMC

STATISTICAL CONSIDERATIONS

All patients enrolled in the study, including those in the run-in phase will be included in the analysis of toxicity and efficacy.

Safety and tolerability is the primary endpoint of this study, and all patients enrolled will be assessed for this endpoint. Adverse events will be recorded and graded based on CTCAE v. 5, and their relationship to the experimental agents reported.

Similarly, all patients enrolled in the study (i.e., the initial 6 patient cohort, and the additional 14 patient expansion) will be included in the efficacy analyses. Clinical responses to the combination of nivolumab, ipilimumab and hypofractionated radiation will be based on RECIST 1.1 criteria. Oncologic outcome endpoints such as progression free and overall survival will be calculated from the date of study enrollment, until disease progression or death from any cause, respectively. Survival estimates will be calculated using the Kaplan-Meier method.

Exploratory endpoints of this study include correlative work performed on research serum and tissue samples.

Sample size determination

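### With exactly 2 DLTs in the 6-patient run-in, the protocol gives conflicting instructions on whether the other 14 patients get the full or the modified regimen

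*Combined protocol and SAP*

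**What the plan says.** Three places in protocol version 3.0 state when the run-in result changes the regimen.

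- **Synopsis, Study Design:** "If more than 2 DLTs (to be defined in Section 5.1.2) are noted in this 6 patient cohort, a dose modification will be implemented".
- **Study Schema (Section 4.2):** "If more than 2 DLTs (to be defined in Section 5.1.2) are noted in this six patient cohort, a dose modification will be implemented".
- **Dosage and Administration (Section 5.1.1)** gives both sides of its cut. For the full regimen: "If ≤ 1 DLT is observed in the run-in phase, then the remaining 14 patients will be provided treatment per the following". For the modified regimen: "If 2 or more DLTs (defined in Section 5.1.2) are observed in the run-in phase, the following treatment will be used".

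The synopsis and Section 4.2 both cite Section 5.1.1 for the modification itself, and a note at the schema sends the reader there for detail on the treatment scenarios. Nothing in the document says which threshold applies if the sections differ.

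**The concern.** This is the only rule that sets the expansion-cohort regimen, and it applies to 14 of the 20 patients. The run-in exists because the triplet with radiation had not been studied, and safety is the primary endpoint. A trigger of more than 2 implies that 2 DLTs leave the full regimen in place. Section 5.1.1 requires the modified regimen at that count. If 2 DLTs occur, the study team must choose between the two texts after seeing the toxicity data, in an open-label single-arm trial.

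The choice also affects what the primary analysis describes. The Statistical Considerations text states: "All patients enrolled in the study, including those in the run-in phase will be included in the analysis of toxicity and efficacy". At exactly 2 DLTs, one reading gives a toxicity estimate for 20 patients assigned to one regimen. The other gives an estimate pooled over 6 patients on the full regimen and 14 on the modified one.

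**Working it through.** **Step 1. Set the rules side by side** (remaining 14 patients, by DLT count in the run-in).

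| DLTs in run-in | Synopsis and 4.2 | 5.1.1 |
|---|---|---|
| 0 or 1 | no modification | full regimen |
| 2 | no modification triggered | modified regimen |
| 3 or more | modification | modified regimen |

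The only disagreement is at exactly 2. It is not a misread symbol: Section 5.1.1 states both sides of its cut consistently, and the other trigger is written out in words in two separate places.

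**Step 2. Look for a clause that settles it.** Section 5.1.2 defines a DLT and sets no cohort threshold. Section 8.4 halts enrollment when more than 3 patients have Grade 4 or higher drug-related toxicity; it does not choose between regimens. The schema note points to Section 5.1.1 for detail but sets no order of precedence.

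**Step 3. Size the difference in exposure** (maximum doses per patient, from the tables in Section 5.1.1).

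| | Full | Modified |
|---|---|---|
| Nivolumab | 12 + 8 = 20 | 6 + 4 = 10 |
| Ipilimumab | 4 | 3 |

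These are the stated caps. Dosing every 4 weeks from week 25 falls in weeks 25, 29, 33, 37, 41, 45 and 49, so 7 rather than 8 doses fit by week 52, and about 12 + 7 = 19 nivolumab doses fit in the year. The contrast with 10 remains large.

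**Step 4. How likely is the disputed result?** The protocol states no operating characteristics for the run-in rule, so there is no figure to reproduce, and it gives no DLT rate. The rates p below are assumptions. Take 6 independent patients and let X be the number with a DLT:

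P(X = k) = C(6, k) p^k (1 − p)^(6 − k)

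At p = 0.30:

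- P(X = 2) = 15 × 0.3² × 0.7⁴ = 15 × 0.09 × 0.2401 = 0.3241
- P(X ≤ 1) = 0.7⁶ + 6 × 0.3 × 0.7⁵ = 0.1176 + 0.3025 = 0.4202, so P(X ≥ 2) = 0.5798
- P(X ≥ 3) = 0.5798 − 0.3241 = 0.2557

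| Assumed p | P(exactly 2) | P(modify), 2 or more | P(modify), more than 2 |
|---|---|---|---|
| 10% | 0.0984 | 0.1143 | 0.0159 |
| 20% | 0.2458 | 0.3446 | 0.0989 |
| 30% | 0.3241 | 0.5798 | 0.2557 |
| 40% | 0.3110 | 0.7667 | 0.4557 |
| 50% | 0.2344 | 0.8906 | 0.6562 |

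The first probability column is the difference between the other two.

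**The case against.** The strongest reply is that Section 5.1.1 already governs. The synopsis and Section 4.2 say what happens above 2 DLTs and never state that the full regimen continues at 2. Only Section 5.1.1 gives an explicit instruction for that count, so following it breaks no literal sentence elsewhere. Both other places point to it, and it is the cautious answer. This is a good reason to choose Section 5.1.1 as the default. It does not remove the conflict: a trigger of more than 2 serves no purpose if the real trigger is 2, and an ordinary reader would take it as the threshold. A pointer to further detail is not a precedence clause.

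Four lesser points deserve a reply.

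- A mix of regimens in the pooled analysis arises by design whenever the regimen is modified, for example at 3 DLTs, and aligning the thresholds does not remove it. This is right. The conflict matters only for whether a mix arises at exactly 2.
- The rules count DLTs, while the binomial counts patients. One patient with two DLTs could reach the disputed count, so the probabilities are illustrative. This stands, but the contradiction does not depend on them.
- Other safeguards exist: individual dose delays under Section 5.1.3, the stopping rule in 8.4 and committee review. They limit risk but do not say which threshold applies.
- Two of the three places say more than 2, and nothing shows which was intended. The default is not neutral either: at an assumed 30% rate it modifies the regimen 58% of the time against 26%. The sponsor should therefore confirm the intent.

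**Conclusion.** The concern holds and must be fixed. At exactly 2 DLTs the run-in rule cannot be carried out consistently as written, and the outcome decides the regimen of 14 of 20 patients, with up to 20 or up to 10 nivolumab doses each. That the texts conflict follows from the wording alone and needs no assumption. How often it would matter rests on assumed DLT rates, independent patients and at most one DLT per patient. On those terms the disputed result has about a 10% chance at a 10% rate, and between one in four and one in three at rates of 20% to 40%.

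**What to change.** State one threshold in the synopsis, Section 4.2 and Section 5.1.1. By default, adopt that of Section 5.1.1: full regimen at 1 DLT or fewer, modified regimen at 2 or more. This changes one phrase in the synopsis and one in Section 4.2. If the sponsor confirms that 3 or more was intended, change both sentences of Section 5.1.1 instead, so that the full regimen continues at 2 or fewer.

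Two optional clarifications could go into the same amendment:

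- Count patients with a DLT rather than DLTs. Section 5.1.2 leans this way, since under-dosed patients without a DLT "will not be taken into account in the assessment of the overall DLT rate for the phase I run-in cohort", but it does not say how several DLTs in one patient count.
- State that the detailed list in Section 5.1.2 overrides its lead sentence, "A DLT will be defined as any Grade 3 or higher toxicity that occurs during the DLT evaluation period", because the list exempts some Grade 3 and 4 events.

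The cost is a wording change submitted to the IRB as a protocol modification (Section 3), with no added patients, data or procedures.
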